9.2 Laboratory Studies During Plasma Exchange

- 9.2.1 During plasma exchange therapy, the following labs will be obtained daily (see Appendix 1):
 - CBC with a differential and platelet count
 - chemistry panel (Na, K, Cl, CO₂, Cr, BUN, Ca, and glucose) with LDH

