9.4 Outpatient/Remission Follow-up and Correlative Laboratory Studies

- 9.4.1 After discharge from the hospital, patients will be seen weekly in the outpatient clinic for the first month. Patients will then be seen monthly for the next 6 months, regardless of which arm of the study they were randomized to (see Appendix 1).

- 9.4.2 The following laboratory studies will be obtained at each follow-up visit:

- CBC with a platelet count
- chemistry panel (Na, K, Cl, CO₂, Cr, BUN, and glucose), total and direct bilirubin
- LDH
- cyclosporine concentration (patient should be told not take their CSA dose until after the blood has been drawn to ensure that we are accurately measuring trough drug levels)

- 9.4.3 In addition patients will have peripheral blood samples (10cc/2 teaspoons) obtained at the same intervals for:

- ADAMTS13 activity
- ADAMTS13 inhibitor assay
- ADAMTS13 antigen level

- ADAMTS13 antibody (IgG) concentration
- VWF multimeric analysis

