9.5 Outpatient Visits

9.5.1 After discharge from the hospital, patients will be seen weekly in the outpatient clinic for the first month. Patients will then be seen monthly for the next 6 months, regardless of which arm of the study they were randomized to. After six months of continuous follow-up patients will then be seen every 3 months for the next 3 years to monitor the course of their disease and obtain laboratory follow-up studies (see Appendix 1)

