10.0 Safety Monitoring During Study

10.0.1 To ensure the safety of all patients enrolled on this study careful monitoring and follow-up for all patients will be an important aspect of this study. At the time patients begin therapy with plasma exchange and either CSA or prednisone, all patients will be hospitalized and monitored for both response to therapy as well as any potential toxicities. Laboratory studies performed daily will monitor the clinical response to therapy, but will also monitor for the earliest signs any other end-organ toxicities (Section 9.1 – 9.4). In the CSA-treated patients the potential for renal toxicity is the primary concern, but patients on both arms will be monitored carefully for this as well as other potential toxicities through daily laboratory as well as daily clinical evaluations. After discharge, patients will continue to be monitored closely in the same manner with laboratory and clinical evaluations at regular intervals as described in Section 9.5 and Appendix 1 of the study protocol.

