10.1 Definition of Adverse Events/Severe Adverse Events

10.1.1 Adverse events as defined in the International Council on Harmonisation Guideline for Good Clinical Practice are described as: “an untoward medical occurrence in a patient or clinical investigation administered a pharmaceutical product that does not necessarily have a causal relationship with this treatment” (ICH E6:1.2).

10.1.2 A serious adverse event is an adverse event that:

- is fatal
- is life threatening (places the subject at immediate risk of death)
- results in inpatient hospitalization or prolonged existing hospitalization
- results in persistent or significant disability/incapacity

- is a congenital anomaly/birth defect
- other significant hazard

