10.2 Reporting of Adverse Events

10.2.1 The principal investigator at each site is responsible for reporting each adverse event to the Protocol Chairman or the study nurse/coordinator coordinating site (Ohio State University Hospital). Contact information is provided in section 16.0 of the study protocol. Adverse events must be reported verbally and faxed to the coordinating site within 7 days of the occurrence using the supplied "Adverse Event" form (see Appendix 3). All serious adverse events must be communicated to the coordinating site verbally within the first 24 hours of the occurrence of the event. The "Adverse Event" form (see Appendix 3) must also be completed and returned to the coordinating site within 7 days of the occurrence of the event. Using these mechanisms of rapid reporting we will be able to rapidly evaluate and minimize the potential risks to patients from the occurrence of these events. Any significant adverse events that potentially would affect other enrolled patients and those yet to be enrolled will be communicating to all participating sites and investigators in a written format and via teleconference if warranted.

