Additionally, we will evaluate several secondary clinical endpoints through this trial, including: 1) exacerbation rate within 30 days post-PE; 2) clinical response rate; 3) the number of PE procedures required to achieve a clinical response; 4) relapse rate; and 5) safety and tolerability of each of the adjuvant treatments to PE. Each of the rates will be calculated assuming that these endpoints are binomially distributed, and 95% confidence intervals generated. For the exacerbation rate endpoint, we will only include those patients who have achieved clinical response (i.e. excluding refractory patients) and compare these rates between the two arms. We will have at least 80% power to detect a difference if the true exacerbation rates are 55% vs. 90% for this subset analysis (not adjusting for multiple comparisons); however, this comparison is distinctly ancillary to our primary clinical interest of achieving treatment success in all patients treated versus only keeping responding patients from experiencing TTP exacerbation. We will also evaluate relapse as a time-to-event variable, where Kaplan-Meier methods will be used to assess time to relapse from last plasma exchange in responding patients. The number of exchange procedures required to achieve clinical response will be assessed between arms using Poisson regression. Safety and tolerability data will be summarized by type of adverse event with frequencies calculated and compared between arms. In addition to these planned quantitative analyses, we will also use graphical

analyses to assess patterns and differences in these factors between the treatment arms.

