Appendix 1. Research Study Calendar

Time (weeks)	0	Day 3										CSA Stop	28
			1***	2	3	4	8	12	16	20	24		
Inpatient Treatment*		→*											
Clinic Visit**			X	X	X	X	X	X	X	X	X	X	
Clinical Studies													
CBC		→*	X	X	X	X	X	X	X	X	X	X	
Platelets		→*	X	X	X	X	X	X	X	X	X	X	
Smear Review													
Chemistry Panel		→*	X	X	X	X	X	X	X	X	X	X	
Total bilirubin	X												
Indirect bilirubin	X												
LDH		→*	X	X	X	X	X	X	X	X	X	X	
Haptoglobin	X												
PT	X												
PTT	X												
Fibrinogen	X												
Direct antibody test	X												
Liver function tests	X												
Cyclosporine Level	X**		X	X	X	X	X	X	X	X	X		
Biologic Samples****	X		X	X	X	X	X	X	X	X	X	X	

*Continue daily until remission and plasma exchange tapered and stopped.

**Cyclosporine levels start on day 3, then weekly until discharge.

*** Weekly visits begin after discharge from hospital.

**** Research samples: 10cc blood, 100cc plasma only at diagnosis at the outset of exchange procedure

[figure not shown]
[figure not shown]
Time (weeks)	40	52	64	76	88	100	112	124	136	148	160
Inpatient Treatment*											
Clinic Visit**	X	X	X	X	X	X	X	X	X	X	X
Clinical Studies											
CBC	X	X	X	X	X	X	X	X	X	X	X
Platelets	X	X	X	X	X	X	X	X	X	X	X
Smear Review											
Chemistry Panel	X	X	X	X	X	X	X	X	X	X	X
Total bilirubin											
Indirect bilirubin											
LDH	X	X	X	X	X	X	X	X	X	X	X
Haptoglobin											
PT											
PTT											
Fibrinogen											
Direct antibody test											
Liver function tests											
Cyclosporine Level											
Biologic Samples****	X	X	X	X	X	X	X	X	X	X	X

*Continue daily until remission and plasma exchange tapered and stopped.

**Cyclosporine levels start on day 3, then weekly until discharge.

*** Weekly visits begin after discharge from hospital.

**** Research samples: 10cc blood, 100cc plasma only at diagnosis at the outset of exchange procedure

Appendix 2. Algorithm for dose adjustment of cyclosporine for both elevated drug levels and renal insufficiency

*reduce cyclosporine dose if not already done. If previously dose reduced and stable serum creatinine, continue at same dose. If cyclosporine was previously held and the serum creatinine is now > 1.5 mg/dl but ≤ 2.5 mg/dl, restart at 50% of planned dose (1.0-1.5 mg/kg).

8.30.07 version

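### Safety is compared between arms only by adverse-event frequency, which is insensitive to a moderate average creatinine rise on cyclosporine and gives no between-arm estimate of recovery, although the data for both are collected

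*Combined protocol and SAP*

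**What the plan says.** Safety of CSA is a secondary objective (1.2). For its analysis, 14.2 states: "Safety and tolerability data will be summarized by type of adverse event with frequencies calculated and compared between arms". The rest of 14.2 adds graphical displays and an interim safety review by the study team and the DSMB, and neither names creatinine. Section 14.3 plans longitudinal models for ADAMTS13 and VWF markers only.

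Section 10.0.1 says of CSA-treated patients that "the potential for renal toxicity is the primary concern, but patients on both arms will be monitored carefully for this".

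The measurements exist:
- At enrolment, creatinine is in the chemistry panel (9.1.1).
- During exchange: "During plasma exchange therapy, the following labs will be obtained daily" (9.2), and the panel includes creatinine.
- At each outpatient visit: "chemistry panel (Na, K, Cl, CO₂, Cr, BUN, and glucose), total and direct bilirubin" (9.4).
- The schedule is common to both arms: "Patients will then be seen monthly for the next 6 months, regardless of which arm of the study they were randomized to" (9.5). Quarterly visits follow for three years, and Appendix 1 carries the chemistry panel past the CSA stop to week 160.

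Adverse events come from the sites: "The principal investigator at each site is responsible for reporting each adverse event" (10.2). Section 10.1 sets no creatinine level at which a rise becomes an event.

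**The concern.** An event count records a rise only if someone calls it an event. A moderate average rise across the CSA arm could stay within normal limits and produce few or no reports. Counts also give no estimate of whether the arms come back together once CSA stops.

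Both questions matter for a nephrotoxic drug given for six months. The pilot experience in section 4.0 shows the difficulty: two CSA patients rose to 1.5 mg/dl, and the authors could not tell whether CSA or TTP was the cause. A randomised comparison adjusted for the enrolment value addresses that ambiguity better than a list of events, and the data for it will be on file. At stake is how informative the secondary safety objective can be.

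**Working it through.** **Size of the trial.** The only planned sample size is for the primary endpoint (50% vs 80%, two-sided 0.05, at least 80% power). With unpooled variance, n = (1.960 + 0.842)² × (0.5×0.5 + 0.8×0.2) / 0.3² = 35.76, so 36 per arm and 72 in total, as in 14.1. No figure is stated for safety, so the steps below show what 36 per arm can do. The documents give no creatinine SD and no steroid-arm renal event rate; those values are assumptions.

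**1. What event counts can detect.** By the pooled normal approximation, power = Φ{[d√n − 1.96√(2p̄(1−p̄))] / √(p₁(1−p₁) + p₂(1−p₂))}, with d the difference and p̄ the mean of the two rates. For 5% vs 30% and n = 36: (0.25×6 − 1.96×0.537) / 0.507 = 0.88, which gives 81% (exact Fisher 76%). For steroid-arm rates of 2%, 5% or 10%, the CSA rate needed for 80% power is 24%, 30% or 38%. The pilot rate was 2/22 = 9%, taking the denominator as the two CSA cohorts (10 in 3.1 plus 12 in 3.2).

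**2. The same shift, counted or measured.** Assume normal creatinine, mean 1.0 mg/dl, SD 0.3, and a shift of 0.2 on CSA.
- Counted above 1.5 mg/dl: 1 − Φ(0.5/0.3) = 4.8% vs 1 − Φ(0.3/0.3) = 15.9%; Fisher power 18%.
- Compared as means: SE = 0.3×√(2/36) = 0.0707; 0.2/0.0707 = 2.83; Φ(2.83 − 1.96) = 81%.

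The mean difference detectable with 80% power is 2.80 × SD × √(2/36), which is 0.13 to 0.33 mg/dl for SD 0.2 to 0.5. This example assumes that everyone shifts equally; if CSA harmed a few patients badly, counts would do relatively better.

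**3. Precision of a baseline-adjusted ratio.** At one visit the 95% CI factor is exp[t × SD × √(1−ρ²) × √(1/36+1/36)], with SD on the log scale and ρ the correlation with the enrolment value.

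| SD | ρ | Factor | 95% CI for a ratio of 1.20 |
|---|---|---|---|
| 0.25 | 0.5 | 1.107 | 1.08 to 1.33 |
| 0.30 | 0.5 | 1.130 | 1.06 to 1.36 |
| 0.40 | 0 | 1.207 | 0.99 to 1.45 |

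A rise from 1.0 to 1.2 mg/dl is below the normal limit of 1.4 in section 4.0 and below the 1.5 mg/dl dosing level in 7.3.3 and 7.5.1. It would usually, though not always, be distinguishable from no effect.

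**4. Precision of proportions.** With equal arms the Newcombe 95% CI for the difference is ±15 points at 3/36 and ±21 points at 11/36. Proportions can therefore only support the model.

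**5. Choices that must be fixed in advance.**
- Threshold: the pilot rises were to 1.5 mg/dl. A cut of >1.5 counts neither, and ≥1.5 counts both.
- Early visits: those rises came after two and four weeks of CSA and normalised after a 50% dose cut, so a display that drops the first weeks could miss them.
- Time origin: "Weekly visits begin after discharge from hospital" (Appendix 1), while CSA starts with exchange and runs six months from its own start. Visit weeks and CSA weeks therefore do not coincide.
- Daily inpatient values: pilot medians were 5 exchanges (CSA) and 6.5 (steroid). With an assumed 3% daily chance of a value ≥1.5, the chance of any such value is 1 − 0.97⁵ = 14% vs 1 − 0.97^6.5 = 18% with no true difference.

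**The case against.** The strongest case is that the plan already has a workable secondary-safety analysis: event frequencies by type compared between arms, graphs, and interim review by the DSMB. Section 10.3.1 follows every adverse event to resolution, so recovery of a reported renal event is tracked. Both arms are monitored for renal toxicity, and unchanged or lower creatinine is part of the remission definition in both (8.1). Nothing in the documents treats a rise within normal limits as important, and the SDs used here are assumed.

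Much of this stands. It limits the point to shifts not reported as events and to the average course after CSA, and it lowers the priority. It does not close the gap: following single events is not a between-arm estimate, and neither the graphs nor the interim review names a creatinine measure.

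A reader might go further and infer that sites will over-report renal events on CSA, so that the planned comparison is biased. The label is open, and creatinine changes the study drug dose in the CSA arm only (7.3.3, 7.5.1), so unequal reporting is possible. The documents do not show it. Both arms are watched, and the definition in 10.1 covers an occurrence that "does not necessarily have a causal relationship with this treatment", so reporting needs no attribution to the drug. The three-day rechecks in 7.4.3 are of CSA trough levels and are not evidence of extra creatinine testing. The effect would also be small: at 9% true events, assumed reporting of 90% vs 70% or 50% gives 0.09×0.20 = 1.8 or 0.09×0.40 = 3.6 points, about one patient in 36. The point does not rest on this.

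**Conclusion.** The point holds in limited form. The only quantitative safety comparison in 14.2 is adverse-event frequency. At 36 per arm that is insensitive to a moderate average creatinine rise, and it yields no estimate of recovery by arm, although creatinine is collected in both arms during and after the planned CSA period. In the worked example the contrast is 18% power for counts against 81% for means; the size depends on the assumed SD, correlation and a uniform shift.

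The documents do not support reading this as absent renal monitoring, as untracked recovery of reported events, or as a threat to the primary analysis. Patient-level monitoring is adequate and the primary analysis is unaffected. It is a cheap improvement of low to moderate priority.

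**What to change.** Add to 14.2, by randomised arm, from data already collected and with time counted from randomisation:

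1. **Main analysis.** Log creatinine at scheduled outpatient visits, adjusted for the enrolment value, reported as a ratio of geometric means with 95% CI in two set windows: from the first outpatient visit (weeks 1 to 4 included) to six months, the planned CSA period; and after six months, the planned post-CSA period.
2. **Supporting table.** Proportion of patients with creatinine ≥1.5 and >2.5 mg/dl at any scheduled outpatient visit, weeks 1 to 4 included, with 95% CI and number assessed. Show daily inpatient values separately.
3. **Switching.** State that prednisone-arm patients who start CSA after an exacerbation (8.5.1) may still be taking it in the post-CSA window, and report how many. Add a sensitivity analysis that drops their values after the switch, labelled as a selected comparison. If half of 36 exacerbate (6 of 12 in the steroid pilot) and half or all of those switch, 27 or 18 controls remain, and the CI factor at SD 0.30 and ρ 0.5 grows from 1.130 to 1.141 or 1.162.

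The cost is one model, one table and SAP wording, with no new samples, visits or staff. State the limits too. Proportions carry about ±15 to 21 points. Dose cuts and switching may dilute a CSA effect. TTP-related renal injury may mask one: with the planned 30-point difference in success and an assumed 10% to 30% of failures reaching 1.5 mg/dl, the prednisone arm gains 0.30×0.10 = 3 to 0.30×0.30 = 9 points. A ratio near 1 would not by itself show renal safety.

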14.3 Statistical Considerations-Correlative Laboratory Studies

The correlative biomarker outcomes described above will be descriptively summarized across and within treatment arms, and patterns in these changes in biomarkers and how they relate to treatment success, relapse, and TTP exacerbation will be explored graphically. For the study to determine the effects of corticosteroids and cyclosporine given individually on serial measurements of ADAMTS13 biomarker profiles and VWF multimeric patterns after their initial therapy and throughout longitudinal follow-up, we will evaluate these biomarkers in relation to the clinical outcomes of interest. For treatment success rates, we will evaluate baseline levels of these biomarkers to identify if there are any associations between these biomarkers and how these patients respond to treatment. These will first be explored graphically, also denoting those patients in the two different treatment arms. Logistic regression for whether or not the patient had a treatment success will be modeled with these baseline biomarkers as well as treatment arm.

In addition, we will compare the changes for each biomarker between the two groups. TTP exacerbations and relapses will be modeled separately. Both of these events are preceded by a period of clinical response where patients exhibit resolution of clinical signs and normal laboratory values. However, as stated above, there are important differences that warrant modeling TTP exacerbation and TTP relapses independently. First, the frequencies of specimen collection are different between the observation periods that lead to the exacerbation and relapses. The patients in the period of initial clinical response are monitored weekly, while the patients in the sustained clinical remission are followed quarterly. Secondly, the underlying pathophysiology for exacerbation and relapse are likely to be different. The disease exacerbation probably represents a continuation of an incompletely resolved disease while relapses of TTP most likely represent a de novo episode of TTP. As a result, the biomarkers that predict TTP exacerbation and relapse are likely to be different.

To examine the potential of the 4 indices (ADAMTS13 activities, ADAMTS13 antigen levels, ADAMTS13 (IgG) autoantibody levels, and antibody inhibitor titers) to predict the recurrences of TTP, we will use the longitudinal data in two ways by separating indices obtained during the sustained clinical remission when they are measured every three months (quarterly) from those indices measured during the initial clinical response when patients are monitored weekly. The data for the relapse analysis will come from all quarterly samples collected from qualified study subjects during sustained remission. The outcome of interest will be whether or not the

individual experiences a relapse of TTP during the three months following the date the measurements are taken. We anticipate obtaining a total of >400 observations that will correspond to approximately >16 events of relapse and other quarterly measurements ($n \sim 400$) without relapses. For analysis of exacerbation in initial clinical remission, the outcome of interest will be whether or not the individual experiences an event of exacerbation in the week following the measurement. The weekly samples in initial clinical remission from the same group of study subjects will be analyzed. We anticipate a total of about 200 weekly data points, corresponding to about >16 measurements with events of exacerbation and 200 measurements without events in the week following measurement. We will use the logistic regression model to analyze all 4 indices independently as well as to evaluate their interacting effects.

Since each individual has several observations, possibly with and without relapse or exacerbation, this would induce a special correlation structure. For this reason, we will introduce random effects into the model (53-55). The covariates corresponding to gender, age, race, and treatment modalities (e.g. CSA vs. corticosteroids) will also be evaluated in the model. Additionally, various variance-covariance structures will be investigated. The Generalized Estimation Equation will also be used if necessary if our specific covariance structures lead to un-interpretable results. Since the number of predictor variables is relatively small, a standard traditional model selection procedure will likely be feasible to study the reach of the predictors as well as their interacting effects. Various model selection criteria such as Ra2, Mallows Cp, AIC, and BIC will be used to evaluate the putative models. In the case where samples are not available on all subjects at consistent timepoints, we will utilize the more flexible growth curve modeling approach to identify changes over time in the biomarker on the incidence and time to relapse as well as TTP exacerbation.

VWF multimer patterns form a relatively complex dataset. We will dissect VWF patterns into several parameters that will all give rise to a continuous measurement. This will be the density of VWF multimers in bands 1 through 15 and the area above band 15. All data will be normalized by the reference plasma included in each gel. For investigating the relationship between ULVWF (area above band 15) and relapse in the quarter immediately following, a logistic regression analysis as described will be performed. Specifically, the response variable will be 1 or 0, depending on whether relapse has occurred or not. The explanatory variable will be the ULVWF value at the beginning of the quarter-interval, with a random effect also included to account for correlations among the different response variable observations over time in a given patient. The effects of other covariates will be included in the model and adjusted for as necessary.

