1.0 OBJECTIVES

This will be a multi-center, open-label, randomized study that directly compares the use of cyclosporine and plasma exchange to corticosteroids and plasma exchange as the initial treatment of patients with thrombotic thrombocytopenic purpura. This study has the following objectives:

Primary Objective

1.1 To determine if cyclosporine given individually as an adjunct to plasma exchange decreases the rate of exacerbation in patients with TTP compared to corticosteroids given as an adjunct to plasma exchange.

Secondary Objectives

1.2 To compare the CSA and PE treatment arm to the corticosteroid and PE treatment arm with respect to:

- exacerbation rate within 30 days post-PE
- clinical response rate
- number of exchange procedures to achieve clinical response
- relapse rate (recurrent disease >30 days after last PE)
- safety data for CSA as an adjunct to PE.
- the effects of corticosteroids vs. cyclosporine on ADAMTS13 antigen, activity, and ADAMTS13 antibody concentration and inhibitor titers using serial measurements both during and after discontinuation of study drug
- the VWF multimeric patterns after initial therapy and throughout longitudinal follow-up between the two treatment arms
- the laboratory biomarker(s) that are prognostic for TTP exacerbation and the risk of relapse

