2.6 Clinical Outcome- Concurrent Corticosteroids and PE as Initial Therapy

A total of 12 patients with idiopathic TTP were treated with corticosteroids and PE. Patients received prednisone at a dose of 1 mg/kg/day concurrently with daily plasma exchange therapy which was continued until remission was achieved (platelet count $>150 \times 10^9/\text{ul}$). PE was then tapered and discontinued with the prednisone tapered over the next 4 weeks. Ten of 12 patients achieved remission after a median of 6.5 daily exchanges, but exacerbations of TTP occurred in 6/10 (60%), comparable to the 50% exacerbation rate from the Oklahoma Blood Institute where steroids were not routinely used. (Table 1) More importantly, there was no significant improvement in ADAMTS13 activity at remission nor suppression of the inhibitor measured within a week of tapering PE. Given these data, we then began to study alternative forms of immunosuppressive therapy as an adjunct to PE.

Table 1.
Clinical and Laboratory Data From Steroid and Plasma Exchange-Treated Patients

Clinical Data	
Remission	10/12
Med. Days to Remission	6.5 (range, 4 to 10)
Exacerbation Rate	6/10 (60%)
Laboratory Data	
Med. Pre-Treatment ADAMTS13	<1% (range, <1 to 5)
Med. Remission ADAMTS13	4% (range, <1 to 72)
Med. Pre-Treatment Inhibitor (ug/ml)	632 (range 188 to 3,574)
Med. Remission Inhibitor (ug/ml)	788 (range 144 to 8,113)

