14.0 Statistical Analysis

14.1 Statistical Considerations-Sample Size Determination

For the study of the primary endpoint (treatment success rate), the sample size required is calculated based on the data from our previous publications. In these previous studies that looked separately at CSA/PE in 10 patients and at corticosteroids/PE in another 10 patients, we saw promising results that led to our hypothesis that CSA/PE treatment for TTP patients results in greater treatment response. In those studies, the primary endpoint was the proportion of patients who had TTP exacerbation, which is a more stringent endpoint that does not include other types of treatment failures such as refractory patients and/or death within 30 days post-PE. In the previous published pilot studies, we showed that 6/10 corticosteroid-treated patients exacerbated versus 0/10 CSA-treated patients. Combined with experience with subsequently treated patients, we observed an overall treatment success rate of 80% and 83% in refractory vs. de novo TTP patients, respectively, treated with CSA+PE versus 33% in those treated with corticosteroids+PE.

In terms of our primary endpoint of treatment success rate, we have designed a phase III trial that compares the proportion of treatment successes in each arm. Specifically, this study design will have at least 80% power to determine a significant difference in the treatment success rates between the arms if the true rates are 50% vs. 80%, assuming a significance level of 0.05 and a two-sided test. This reflects a clinically meaningful difference, and the data from our previous studies and experience support it as a feasible difference to detect. We plan to enroll a total of 72 patients to this trial (36 to each arm) to test the null hypothesis that there is no difference in treatment success rate between these treatments.

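### Section 14.3 compares biomarker changes between arms with no stated scale and no baseline adjustment; a log-scale, baseline-adjusted comparison would be more efficient and needs no new data

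*Combined protocol and SAP*

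**What the plan says.** Section 1.2 lists as a secondary objective a comparison of the arms on "the effects of corticosteroids vs. cyclosporine on ADAMTS13 antigen, activity, and ADAMTS13 antibody concentration and inhibitor titers using serial measurements". Section 14.3 is where that objective is analysed. It begins with descriptive summaries and graphs, and then gives the only between-arm analysis in which a biomarker is the outcome: "In addition, we will compare the changes for each biomarker between the two groups". No test, measurement scale, visit or covariate follows.

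The other models in section 14.3 answer different questions. The logistic model with baseline biomarkers has treatment success as its outcome. The random-effects, GEE and growth-curve methods are aimed at exacerbation and relapse. The covariates listed for them are gender, age, race and treatment.

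The only biomarker spread in the documents is Table 1 in section 2.6, from the steroid pilot cohort. The pre-treatment inhibitor is "632 (range 188 to 3,574" and the remission inhibitor is "788 (range 144 to 8,113", both in ug/ml. Pre-treatment ADAMTS13 activity is "<1% (range, <1 to 5", so its lower end lies below the limit of measurement. The trial is sized on the primary endpoint alone: "We plan to enroll a total of 72 patients to this trial (36 to each arm". No SD, correlation, effect size or power is stated for any biomarker.

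**The concern.** This comparison tests the mechanism behind the trial, namely that cyclosporine suppresses the inhibitory antibody (section 3.3). The sample size was not chosen for it, so there is no spare power.

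Two choices are left open, and both affect efficiency. First, a change score subtracts the whole baseline value. That is the best weight only when the regression slope of follow-up on baseline is 1; otherwise it adds noise that a baseline-adjusted analysis avoids. Second, in strongly right-skewed data a mean difference in ug/ml is governed by a few very high values.

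Leaving scale and visit open also allows the analysis to be chosen after the data are seen.

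**Working it through.** **The plan's own figure.** Section 14.1 claims "at least 80% power to determine a significant difference in the treatment success rates between the arms if the true rates are 50% vs. 80". The test there is two-sided at the 5% level. The unpooled two-proportion formula gives (1.960 + 0.842)² × (0.25 + 0.16) / 0.30² = 35.8, so 36 per arm. That reproduces the total of 72. There is no biomarker figure to reproduce.

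**Skewness (Table 1).**
- Pre-treatment: 3,574 / 188 = 19.0-fold. The median of 632 lies 444 above the minimum and 2,942 below the maximum.
- Remission: 8,113 / 144 = 56.3-fold. The median of 788 lies 644 above the minimum and 7,325 below the maximum.

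**Log-SDs inferred from the ranges.** SD = ln(max/min) divided by the expected range of a normal sample (3.258 for n = 12, 3.078 for n = 10).
- Pre-treatment: s0 = 2.945 / 3.258 = 0.90.
- Remission: s1 = 4.031 / 3.078 = 1.31.

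The sample sizes 12 (treated) and 10 (in remission) are assumed to apply to the laboratory values.

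**Residual variances on the log scale, at correlation ρ.**
- Change score: s0² + s1² − 2ρ·s0·s1.
- Baseline-adjusted: s1²(1 − ρ²).

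The two are equal when ρ = s0/s1 = 0.90/1.31 = 0.69.

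**Assumptions for power.** Lognormal values, 30 evaluable patients per arm out of 36, a true halving (ln 2 = 0.693), two-sided 0.05, and ρ over a range because the documents give none. Power comes from simulation; repeat runs agree to within about 2 points.

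| ρ (assumed) | Variance, log change | Variance, log adjusted | Ratio | Power, untransformed change, t-test | Power, log change | Power, log baseline-adjusted |
|---|---|---|---|---|---|---|
| 0 | 2.533 | 1.715 | 1.48 | 23% | 37% | 52% |
| 0.2 | 2.059 | 1.647 | 1.25 | 27% | 46% | 53% |
| 0.4 | 1.585 | 1.441 | 1.10 | 31% | 56% | 59% |
| 0.6 | 1.112 | 1.098 | 1.01 | 37% | 72% | 72% |

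As a check by formula at ρ = 0, power ≈ Φ(0.693/√(2V/30) − 1.96). This gives Φ(1.687 − 1.96) = 39% for log change and Φ(2.050 − 1.96) = 54% for the adjusted analysis, close to the simulation.

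**Separating the two causes.**
- Baseline adjustment, already on the log scale, adds 15, 7, 3 and 0 points (last column minus the one before).
- Taking logs of an unadjusted change adds 14, 19, 25 and 35 points.
- Adjusting for baseline on the untransformed scale helps little: with 36 per arm, power moves from 27% to 34% at ρ = 0 and from 38% to 39% at ρ = 0.5.

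**Sensitivity to the SDs.** The adjustment effect depends on the SD ratio. If both log-SDs were equal, a change score would have 51% power at ρ = 0, 62% at 0.3, 68% at 0.5 and 73% at 0.7 in a setting where the adjusted analysis has 80%. With the Table 1 SDs the corresponding figures are 64%, 74%, 78% and 80%.

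**The case against.** The strongest reply is that section 14.3 does not describe a poor analysis; it describes very little. Log change, percentage change or a baseline-adjusted model would all fit its wording. That is right. A reader might infer that the plan commits to untransformed differences, but no such word appears. The fault is an open choice, one reading of which is costly.

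A reader might also infer that missing baseline adjustment costs about half the power. The documents do not support that. A gap of about half (for example 27% against 53% at ρ = 0.2) appears only when an untransformed change is compared with an adjusted log-scale analysis, so that scale and adjustment change together.

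It can further be said that the inputs are weak, and they are. The 19- and 56-fold ranges are one marker at two times in one small cohort. Each SD rests on two extreme values; by the same normal-range method, 95% intervals are about 0.60 to 1.57 and 0.84 to 2.41. No correlation is given. It might be argued that plasma exchange weakens the link between baseline and follow-up, but the documents do not show this. Sections 2.3 and 2.6 report little or no fall in inhibitor with exchange, which settles nothing about correlation either.

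Finally, this is a correlative secondary analysis with no stated power, and the primary result is untouched. That limits the importance of the point but does not remove it, since the better analysis uses values the change comparison already needs.

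**Conclusion.** The point holds as a matter of efficiency and pre-specification. The sole between-arm biomarker comparison leaves the scale open and makes no baseline adjustment. It is not biased under randomisation.

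Under the stated assumptions, adjustment alone is worth about 15 points of power at a correlation of 0 and nothing at 0.6. Fixing the log scale is worth about 14 to 35 points relative to a t-test on untransformed change. At a correlation of 0 the two contribute about equally; from 0.2 upward the scale dominates.

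These sizes rest on lognormal values, log-SDs read from pilot ranges, 30 evaluable patients per arm, a halving of the marker and assumed correlations. They also treat the Table 1 inhibitor in ug/ml as the IgG antibody concentration of section 13.2. They illustrate the pattern and should not be carried over to activity, antigen or Bethesda titre.

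**What to change.** Replace the sentence in section 14.3 with a specified analysis:

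- **Model.** Regress the log follow-up value on arm, log baseline value and recurrent/de novo status (the stratification factor in section 14.2), at named scheduled visits. An alternative is a repeated-measures model with baseline as an outcome and a common baseline mean. It keeps patients without a pre-exchange sample, which can arise because section 5.4.2 allows enrolment up to 48 hours after the first exchange.
- **Reporting.** Ratios of geometric means with 95% confidence intervals.
- **Values below detection.** State a rule for activity and for the Bethesda titre (sections 13.1 and 13.3), since an undetectable titre has no logarithm. Examples are setting such values to the limit or using a censored-data model.
- **Steroid-arm patients who receive cyclosporine for an exacerbation (section 8.5.1).** State how their later visits enter the between-arm comparison. Section 8.5.1 separates them from the upfront cyclosporine group but does not say this.
- **Baseline values.** Section 9.1.2 lists activity, inhibitor and antigen at enrolment; IgG antibody and VWF multimers appear only in the follow-up list (section 9.4.3). Confirm that these two are also measured on the enrolment sample. A change score needs the same values.

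The cost is SAP wording and slightly more analysis work. No new data are needed beyond what comparing changes already requires.
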